#### Calculation,

Adjusting for Dropout (20%)

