#### **Final Sample Size**

- 55 participants per group
- Total: 110 participants (both groups combined)

28.02.2025

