#### Collection of blood samples

• Table 1 summarizes the blood sample collection. The investigations will be done at the North Colombo Teaching hospital which is an accredited laboratory. These tests are required to assess the efficacy and safety of the medications in an objective manner.

Table 1: Summary of Blood Sample Collection

Day	Blood volume	Investigations
Enrolment	6 ml	FBS, Liver profile  Lipid profile, Serum HCG (Female participants only)
Allocation Visit - Beginning of 1 st Month	6 ml	FBS Serum HbA1c Fasting serum insulin

28.02.2025

		Lipid profile, Liver profile, Total bilirubin
		Serum creatinine
		FBC
		Serum electrolytes
3 rd month and 6 th month	6 ml	FBS
		Serum HbA1c
		Fasting serum insulin
		Lipid profile, Liver profile, Total bilirubin
		Serum creatinine
		FBC
		Serum electrolytes

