## 4.8. Data analysis:

Data will be analyzed using SPSS software version 21. Baseline patient characteristics will be described using descriptive statistics. Continuous variables will be expressed using mean and standard deviation or median with range depending on the distribution of data. Categorical variables will be expressed using frequency and percentage. Primary analysis will be done using a modified intention to treat (mITT) analysis where only subjects with at least one follows up assessment done will be included in the analysis.

Mean change in CAP score and LSM from baseline to 6 months will be compared between the 2 groups (Caffeine tablets vs placebo) using Independent T test or Mann Whitney U test depending on the distribution of data. For the secondary endpoints continuous variables will be compared using Independent T test or Mann Whitney U test and categorical variables will be compared using Chi square test. Repeated measures ANOVA will be used for analysis of change in variables from baseline till end of study. P value less than 0.05 will be considered statistically significant.

Safety outcomes will be described using descriptive statistics. For patients who were lost to follow up, the last available value will be used for analysis.

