#### Safety and adverse event data analysis

28.02.2025

Vital sign measurements and laboratory biochemical test data will be presented as mean and standard deviation.

A listing of all adverse events by participants including % of participants who experienced adverse events will be presented. This list will include adverse event (actual term and preferred term), event start and end dates, category as per the ICH Topic E 2 A Clinical Safety Data Management: Definitions and Standards for Expedited Reporting, relationship to study drug/procedure, seriousness, and outcome.

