#### 5.5. Follow up assessment

The recruited patients will be advised to come for monthly assessments and will be asked to attend the nearest hospital, if they develop any complications and inform the study team of such incidence.

The degree of adherence to prescribed lifestyle changes and diet will be recorded at the baseline and monthly follow-up visits. Physical activity and alcohol consumption will also be monitored at the baseline and monthly follow-up visits.

Anthropometric measurements, physical examination and vital sign measurements (BP, HR, RR etc..) will be monitored at the baseline and each monthly visit. Details on concomitant medications will be recorded in monthly visits.

Liver profile, Lipid profile, Full blood count, Serum creatinine, fasting blood glucose, HbA1c, serum insulin, serum electrolytes and urine analysis and serum insulin will be investigated at the baseline, at 3 months and 6 months.

Fibro scan will be done at the baseline and after 6 months at the completion of the study.

The details of items which will be measured on every visit are described in Table 2.

Table 2: Summary of follow up

	Enrolment	Allocation 1	Subsequent visits							
TIME POINT		0	1 st	2 nd	3 rd	4 th	5 th	6 th		
			mont	mont	month	mont	month	mont		
			h	h		h		h		
ENROLMENT										
Eligibility screen	×									
Informed consent	×									
Allocation		×								
INTERVENTIO										
NS										
caffeine or		×	×	×	×	×	×			
placebo										
ASSESSMENTS										
Medical history	×	×	×	×	×	×	×	×		
taking										
AUDIT	×	×	×	×	×	×	×	×		
FFQ and IPAQ	×	×	×	×	×	×	×	×		

Height, weight			×	×	×	×	×	×
and waist								
circumference								
Blood pressure	×	×	×	×	×	×	×	×
Physical examination 	×	×	×	×	×	×	×	×
USS scan	×							
Fibro scan		×						×
FBG	×	×			×			×
Fasting serum insulin		×			×			×
HCG only female	×							
Serum HbA1c		×			×			×
Lipid profile	×	×			×			×
Liver enzymes	×	×			×			×
Total bilirubin	×				×			×
Serum creatinine		×			×			×
Serum electrolytes		×			×			×

FBC	×		×		×
UFR	×		×		×

28.02.2025

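### The unrestricted last-value rule in section 4.8 would place pre-dose bloods of patients lost before month 3 in the on-treatment laboratory safety means

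*Protocol*

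**What the plan says.** The last paragraph of the general text in section 4.8 has two sentences. The first is "Safety outcomes will be described using descriptive statistics". The second is "For patients who were lost to follow up, the last available value will be used for analysis". The second names no variable, endpoint or analysis to which it is confined.

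The subsection on safety and adverse event data, still within 4.8, then states: "Vital sign measurements and laboratory biochemical test data will be presented as mean and standard deviation". It gives no exception to the last-value rule and does not say which values count as on treatment.

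Section 5.5 lists the laboratory panel (liver and lipid profiles, blood count, creatinine, electrolytes, glucose measures, urine) and says that it "will be investigated at the baseline, at 3 months and 6 months". Tables 1 and 2 agree that no bloods are due at months 1 and 2. Section 4.6 gives the panel both purposes: "These tests are required to assess the efficacy and safety of the medications in an objective manner".

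The modified intention-to-treat restriction in 4.8 ("only subjects with at least one follows up assessment done will be included in the analysis") is stated for the primary analysis only.

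**The concern.** The rule and the schedule combine badly. The month-0 bloods belong to the allocation visit, when the first bottle is handed out, so they precede the first tablet. For anyone lost before month 3 they are also the last scheduled bloods. Carrying them forward reports a result taken before any exposure as a month-3 or month-6 result on caffeine or placebo.

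Assessing side effects is a secondary objective (section 2.2), and section 7 counts biochemistry and haematology among the safety parameters. The laboratory means are thus part of how the trial will describe safety, and invented zero changes pull them towards baseline. The wider problem of carry-forward for the FibroScan endpoints is separate: a repair worded only for CAP and LSM would leave this sentence in force for the laboratory data.

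**Working it through.** **Inputs.** Planned dropout 20% and "55 participants per group" (section 4.4). Bloods at baseline, month 3 and month 6 (section 5.5, Tables 1 and 2). The share of dropouts lost before month 3 is not given; 25%, 50% and 100% are assumed below.

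**The plan's own figure.** The standard two-group formula with SD 5, difference 3, two-sided 5% and 80% power gives 2 × 25 × (1.96 + 0.84)² / 9 = 43.6, so 44 per arm. Then 44 / 0.80 = 55 per arm and 110 in total, as stated. (The printed formula lacks the factor 2 and the square on the difference, but the stated size is reproduced.)

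**Dilution.** Let f be the share of an arm with only pre-dose bloods, and d the mean change at month 3 in those measured. The carried-forward change is 0, so the reported mean change is (1 - f) × d + f × 0 = (1 - f) × d. This does not depend on why patients leave.

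| Share of the 20% dropout lost before month 3 (assumed) | f | Patients per arm of 55 | Reported change / change in measured patients |
|---|---|---|---|
| 25% | 5% | 2.75 | 0.95 |
| 50% | 10% | 5.5 | 0.90 |
| 100% | 20% | 11 | 0.80 |

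The table takes all patients in the arm as the denominator, since no separate safety set is stated. Using the primary-analysis set would remove those lost before any follow-up visit, but not those who attend month 1 or 2 and are then lost.

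**Month 6.** Patients lost after month 3 carry a month-3 value, which is an on-treatment value. If 10% of the arm is lost before month 3 and 10% after it, and the month-3 change is a fraction r of the month-6 change, the factor is 0.80 + 0.10r: 0.85 at r = 0.5 and 0.90 at r = 1.

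**If early leavers differ.** Suppose, as an assumption only, that those lost before month 3 would have had twice the change of those who stay. With the stayers' change set to 1, the true mean is (1 - f) + 2f = 1 + f. Carry-forward shows 1 - f; as-observed means show 1.

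| f | Shortfall with carry-forward, 2f/(1 + f) | Shortfall as observed, f/(1 + f) |
|---|---|---|
| 5% | 9.5% | 4.8% |
| 10% | 18.2% | 9.1% |
| 20% | 33.3% | 16.7% |

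Half of the shortfall remains after the repair in every row.

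**The case against.** The strongest reply is that the rule closes the general analysis text, whereas safety has its own subsection with its own method that never invokes it. Safety is to be described, while the rule concerns values used for analysis, so it could be read as covering the comparative analyses only. Safety sets and treatment windows are also commonly left to a statistical analysis plan, which is not at hand. This shows that the text is open to a narrower reading; it does not restrict the rule. The protocol is not silent here: it fixes a rule without scope, next to the safety sentence, and 4.8 requires ethics committee approval for departures from the statistical plan.

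A reader might go further and infer that the rule hides harm in the caffeine arm, because people who feel unwell leave and are replaced by a normal baseline result. The documents do not support that:

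- The rule names patients lost to follow-up. Section 7.7 treats withdrawal separately and asks for reasons, adverse events among them.
- No eligibility criterion requires normal liver enzymes. The secondary endpoints expect AST, ALT and GGT to fall, so for these the carried-forward value would dilute an expected benefit.
- No summary of the share of patients above a limit is planned, so no dilution of such a share can be claimed.
- Vital signs are taken monthly, so only patients lost before the month-1 visit would carry a pre-dose value.
- Adverse events are asked about at every monthly visit and listed with percentages, individual laboratory limits govern the stopping of dosing, and the safety board reviews safety data. None of these depends on the rule.

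These limits stand. They reduce the reach of the point to the laboratory means, but do not remove it.

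**Conclusion.** The point holds for the laboratory safety means. Followed literally, section 4.8 puts pre-dose values of patients lost to follow-up before month 3 into the month-3 and month-6 summaries. The mean change then shrinks to 0.95, 0.90 or 0.80 of that in measured patients at 5%, 10% or 20% early loss. At month 6 this factor also assumes that patients lost after month 3 carry a change equal to that in patients measured at month 6.

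The early share is an assumption throughout, and 20% (11 of 55) is reached only if all planned dropout is loss to follow-up and all of it occurs before month 3. The direction of any bias beyond this dilution depends on why patients leave, which the protocol cannot tell us. This is a stated rule that yields a wrong descriptive summary. It should be corrected, but it does not disable the trial's detection of harm.

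**What to change.** Add to section 4.8: 'The last-value rule does not apply to safety data. Laboratory safety values are summarised by arm and visit as observed, with the number of patients measured. No value taken before the first tablet enters an on-treatment summary.' If the carry-forward rule is rewritten for the FibroScan endpoints, the same amendment can carry this wording.

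A summary of each patient's most abnormal value after the first tablet would be a useful addition, but is optional and not needed to correct the error.

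The cost is a few sentences, with no new data or visits. The n per visit will be visibly smaller. As-observed means do not recover the unmeasured values of early leavers, so the n should be read alongside the adverse event listing and the reasons for withdrawal.

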#### Safety and adverse event data analysis

28.02.2025

Vital sign measurements and laboratory biochemical test data will be presented as mean and standard deviation.

A listing of all adverse events by participants including % of participants who experienced adverse events will be presented. This list will include adverse event (actual term and preferred term), event start and end dates, category as per the ICH Topic E 2 A Clinical Safety Data Management: Definitions and Standards for Expedited Reporting, relationship to study drug/procedure, seriousness, and outcome.

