#### **Secondary endpoints**

- 1. Reduction in Anthropometric parameters: waist circumference, weight and body mass index (BMI) from baseline to week 24.
- 2. Reduction in levels of Aspartate Transaminase (AST), Alanine Transaminase (ALT) and Gamma Glutamyl Transpeptidase (GGT) from baseline to week 24.
- 3. Reduction in fatty liver index (FLI) from baseline to week 24.

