#### Criteria for stopping the trial or discontinuation of study intervention

28.02.2025

Individual subjects dosing will be stopped immediately if clinically relevant allergic reaction/ hypersensitivity occurs which needs medical intervention.

- 1. Dosing will be stopped if liver enzymes increases > 3 x normal range
- 2. Dosing will be stopped if conjugated bilirubin increases > 1.5 x normal range
- 3. Dosing will be stopped if serum creatinine increases > 1.5 x normal range
- 4. Dosing will be stopped if subjects suffer from a drug related (assessed as possibly or probably) and clinically relevant AE of moderate or severe intensity.
- 5. Any clinically significant values outside the reference ranges with major deviation and/or possible pathological relevance in physical examination, biochemical examination, hematology, vital signs measurements, electrocardiogram (ECG), and urinalysis.
- 6. Patients with AUDIT score > 8.

A volunteer can decide to withdraw from study participation at any time, for any reason, specified or unspecified, and without penalty or loss of benefits to which the subject is otherwise entitled. In this case, the subject must immediately contact the investigator and state that he is leaving the study.

Reasons for the withdrawal of the study (AE, ineffective treatment, inability to comply with the study requirements etc.) will be sought, if the patient is willing to provide that information. They will be made aware that their decision will in no way affect their treatment, and that they will be free to withdraw from study at any time. To respond to questions and record complaints during the study, contact details of two investigators will be provided to the study participants. Patient can be withdrawn from the study upon the principal investigator's decision to terminate the study, based on study compliance and adverse reactions development such as low rates of compliance, complications, or inability to tolerate the medication etc.

28.02.2025

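### Laboratory safety is fixed as mean and SD, and nothing counts the participants who cross the protocol's own enzyme and creatinine stop limits

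*Protocol*

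**What the plan says.** Section 4.8, under the safety and adverse event heading, gives one summary for laboratory data: "Vital sign measurements and laboratory biochemical test data will be presented as mean and standard deviation". The same heading adds individual-level output for adverse events: "A listing of all adverse events by participants including % of participants who experienced adverse events will be presented". The fields of that list end with "relationship to study drug/procedure, seriousness, and outcome". They include no laboratory value and no dosing stop. Earlier in 4.8 there are two general rules: "Safety outcomes will be described using descriptive statistics" and "Categorical variables will be expressed using frequency and percentage".

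Section 7.7 sets laboratory limits for the individual participant. Two of them read "Dosing will be stopped if liver enzymes increases > 3 x normal range" and "Dosing will be stopped if serum creatinine increases > 1.5 x normal range". A third concerns conjugated bilirubin at 1.5 times the normal range.

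Section 2.4 makes reduction in AST, ALT and GGT to week 24 a secondary endpoint. Creatinine is not an endpoint; section 4.6 lists it among the tests done for safety. Section 5.5 and Table 2 schedule liver enzymes and creatinine at baseline, month 3 and month 6.

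**The concern.** The protocol recognises laboratory harm in the individual but summarises it through the group average. A mean and SD cannot say who crossed a limit, or how many did in each arm. Yet assessing side effects of caffeine is a stated secondary objective (section 2.2).

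The difficulty is sharper for the enzymes. The same average serves as the safety summary and as a measure of hoped-for benefit, so a modest fall in most participants can outweigh a large rise in a few. An arm with several stop-level rises could then show improved mean enzymes. For creatinine no fall is expected, and the problem is only that a few large values are spread over the whole arm.

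Timing adds to this. With scheduled bloods at months 3 and 6 only, a participant who crosses at month 3 and stops dosing may be back in range by month 6 and leave no trace in the month 6 mean.

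**Working it through.** **Arm size (section 4.4).** With SD 5, difference 3, two-sided alpha 0.05 and 80% power, the standard two-sample formula gives 2 × 25 × (1.96 + 0.84)² / 9 = 43.6, so 44 per arm. Allowing for 20% dropout, 44 / 0.80 = 55, which is the protocol's figure. I use 55 per arm, and 44 where only completers count.

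**Assumed values, not in the protocol.** The limits are read as multiples of the upper limit of normal. That upper limit is taken as 40 U/L for an enzyme, so a participant at 40 U/L must rise by just over 80 U/L to exceed three times it. The SD of change in the other participants is 20 to 30 U/L.

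**Arm mean change**, with k participants rising by 80 and the other 55 − k falling by 5 U/L: [80k − 5(55 − k)] / 55.
- k = 1: (80 − 270) / 55 = −3.5 U/L
- k = 2: (160 − 265) / 55 = −1.9 U/L
- k = 3: (240 − 260) / 55 = −0.4 U/L

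Up to three stop-level rises are still reported as a mean fall. With two crossers the result depends on the fall in the other 53: no fall gives 160 / 55 = +2.9 U/L, and a fall of 10 gives (160 − 530) / 55 = −6.7 U/L.

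**Fall in the others that cancels the crossers:** 80k / (55 − k), which is 1.5, 3.0 and 4.6 U/L for one, two and three. With wider assumptions (crosser at 125 U/L, baseline mean 40 to 60, 44 to 55 per arm) the figures are 1.2 to 2.0, 2.5 to 4.1 and 3.8 to 6.2 U/L.

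**Against sampling error.** Two crossers move the arm mean from −5.0 to −1.9, a shift of 3.1 U/L. The standard error of one arm's mean change is 20/√55 = 2.7 to 30/√55 = 4.0 U/L. For the difference between arms it is 20√(2/55) = 3.8 to 30√(2/55) = 5.7 U/L. The shift is below one standard error of the between-arm comparison.

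**What the SD shows.** With two crossers the mean is −1.91, so the variance is (53/55)(SD² + 3.09²) + (2/55)(81.91²). An SD of 20 becomes about 25, and 30 becomes about 33.5. The SD reacts, but the number of crossers cannot be read from it.

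**Creatinine** (assumed mean 0.9 mg/dL, crosser at 1.85 mg/dL). One crosser moves the arm mean by 0.95 / 55 = 0.017 mg/dL (0.022 with 44), and three by 0.052 (0.065 with 44).

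**What a count shows.** Each crosser is 1/55 = 1.8% of an arm, or 1/44 = 2.3% of completers, and is directly visible.

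**Whether adverse event reporting fills the gap.** Section 7 obtains adverse event information through general questions or spontaneous complaints. Section 7.1 defines every severity grade by symptoms, so a symptom-free laboratory rise has no defined grade. No section requires a limit crossing to be recorded as an adverse event. On the case report form (Annexure 1C) the box for discontinuation sits among the adverse event items, so it depends on an event having been entered.

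**Bilirubin.** Section 7.7 limits conjugated bilirubin, but Tables 1 and 2 name only total bilirubin.

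**The case against.** The strongest objection is that this is only a missing table. Threshold counts and shift tables are commonly left to a statistical analysis plan, which is not at hand, and the general rules in 4.8 on descriptive safety statistics and on categorical variables would permit them. That much is right: mean and SD is a valid summary, and the protocol does not say that nothing else may be produced. But the point rests on what is stated. The one summary named for laboratory safety data cannot show the events that section 7.7 defines. It is also narrower than the mean and SD, or median with range, that 4.8 gives for continuous variables generally. A range would at least show the maximum, and might do so for the enzymes as secondary endpoints, though still without a count.

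A reader might infer that crossers disappear altogether. The documents do not support that. Each would be identified so that dosing could be stopped. Section 7.4 collects observed as well as spontaneously reported events, so an excursion recorded as one would be listed. The data safety monitoring board reviews safety data, and the SD would widen. None of these, however, commits the trial to report a number by arm.

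A reader might also infer that creatinine is masked by an expected fall. Nothing in the protocol predicts one. Finally, crossers confined to the caffeine arm would push the between-arm enzyme comparison towards harm, so a single-arm figure overstates how easily they are missed. That is fair, but in the illustration the push is less than one standard error.

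**Conclusion.** The point holds in a limited form. As written, laboratory safety reporting cannot show how many participants in each arm crossed the protocol's own limits. For AST, ALT and GGT a fall in the mean can mask a few stop-level rises; for creatinine they are diluted. In the illustration two such rises leave a mean fall of about 1.9 U/L. This rests on the assumed upper limit of 40 U/L, the 80 U/L rise and the 5 U/L fall in the others; the mechanism does not depend on those exact values. The adverse event listing may capture these cases but is not bound to.

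This weakens reporting on the side-effect objective. It does not affect the primary comparison or the sample size, and it does not show that harm would go unnoticed during the trial. No view is taken on whether the section 7.7 limits are the right ones.

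**What to change.** Add to the safety part of section 4.8: by arm, the number and percentage of participants whose worst post-baseline value, scheduled or unscheduled, crosses each section 7.7 limit for liver enzymes and creatinine, with a baseline-to-worst shift table. Use the limits as section 7.7 words them and state the denominator. Keep mean and SD as supportive.

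Reconcile the conjugated bilirubin limit in section 7.7 with the total bilirubin named in Tables 1 and 2; until then that limit cannot be counted from the scheduled tests.

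The cost is one extra table. For enzymes and creatinine the scheduled data are already planned; unscheduled results need only be entered when they occur. No visit, sample size or limit changes.

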#### 4.6. Data collection:

- Data collection will be done by a two MBBS qualified graduates, who can converse in Sinhala, English and Tamil and are trained by the consultant hepatologist.
- An interviewer administered questionnaire will be used to record basic demographic details of the patient in addition to the data on clinical features. Patient identification data is collected for the purpose of tracing the patient in an adverse event or a medical

28.02.2025

- emergency. However, personal identification will not be used in the database, and the serial numbers will be used instead of names.
- Data collection will be done using a Case Report Form developed by the investigators.
   During each monthly visit, investigators will query regarding any adverse effects. Patients will also undergo clinical examination on visits.

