#### 7.1. The severity of adverse events is characterized as follows

Mild: Any symptom of which the subject is aware, but which is easily tolerated.

**Moderate:** Any symptom which is discomforting enough to cause interference with a volunteer's usual activity.

**Severe:** Any symptom which causes a volunteer's inability to perform usual activity For all AEs, information will be obtained to determine causality.

The causal relationship between the investigational caffeine product and the AE will be characterized according to the following:

**Not related** – there is not a reasonable possibility that the study drug caused the AE.

**Unlikely** – suggests that only a remote connection exists between the study drug and the event. Other conditions, including concurrent illness, progression or expression of the disease state or reaction to concomitant medication, appear to explain the AE.

**Possible** – suggests that the association of the AE with the study drug is unknown, however the event is not reasonably supported by other conditions.

**Probable** – suggests that a temporal sequence of the AE with drug administration exists and, in the Investigator's clinical judgment, it is likely that a causal relationship exists between the drug administration and the AE, and other conditions (concurrent illness, progression or expression of the disease state, or concomitant medication reactions) do not appear to explain the AE.

Events where a causal relationship is classified as probable or possible will be regarded as related.

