#### 7.2. Outcome

The outcome of the adverse event will be classified according to the following definitions:

**Recovered / resolved:** the event has resolved (no further symptoms are present, and no treatment is being received by the subject).

Recovered / resolved with sequelae: the event has resolved but lingering effects may be present.

**Fatal** / **life threatening:** the subject died as a result of the event. This code should only be used for the event that caused the death, not any event that was present at the time of the subject's death.

28.02.2025

**Unknown:** will be used in the event that the subject is lost to follow-up and no reliable data can be obtained.

All observed AEs will be reported as described in the following sections.

Medically qualified investigators will obtain appropriate information to determine the outcome of the AE and to assess whether it meets the criteria for classification as a Suspected Unexpected Serious Adverse Reaction (SUSAR) requiring immediate notification.

The codes can be accessed all 24hrs and in the event of a SAE when the code of that patient will be broken.

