## Followed treatment

- 0–6 days  $\rightarrow$  No adherence
- 7–13 days  $\rightarrow$  Poor adherence
- 14–20 days → Moderate adherence
- 21–27 days  $\rightarrow$  Good adherence
- 28 days (Every day) → Complete adherence

Adverse Events (AE) R	eporting:				
• Any AE observed?	☐ Yes		□ No		
• If yes,					
1. Degree:					
Mild: □	Moderate: □		Severe: □		
2. Relation to treat					
Non	Unlikely:	Possible:	Probable:		
Related: □					
3. Outcome:					
Recovered/resolved: □	Recovered/resolved: □				
Recovered/resolved with	Recovered/resolved with sequelae: □				
Fatal/Life threatening: □	Fatal/Life threatening: □				
Unknown: □					
4. Action Taken:					
No action□	Medical				
Discontinued□	Intervention□ Discontinued□				

Reported: □			
Summary of the event	t :		

28.02.2025

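### The adverse-event form has no field for term, dates or seriousness that the planned listing needs, and its outcome codes contradict their definition and omit ongoing events

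*Protocol*

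**What the plan says.** The protocol's section on safety and adverse event data analysis (within 4.8) commits to a listing of adverse events by participant, with the percentage of participants affected. Of its content it says "This list will include adverse event (actual term and preferred term), event start and end dates", then a category under ICH E2A, and "relationship to study drug/procedure, seriousness, and outcome".

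Section 4.6 names the instrument: "Data collection will be done using a Case Report Form developed by the investigators". The form is Annexure 1C (section 11.7). Its adverse-event block opens with the yes/no item "Any AE observed". It then has four numbered items (degree, relation to treatment, outcome, action taken), a box for whether the event was reported, and a free-text field, "Summary of the event".

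The form offers four outcome codes: recovered/resolved, recovered/resolved with sequelae, "Fatal/Life threatening", and unknown. Section 7.2 defines the third by "the subject died as a result of the event" and restricts it to the event that caused the death. It reserves the fourth for participants lost to follow-up with no reliable data.

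**The concern.** The form and the planned listing were not written to match. Seriousness is one of the items to be listed, yet the form nowhere asks for it. Nor does it ask when an event began or ended, or what it was called. Nothing ensures that these are recorded in the same way for every participant, and onset dates and seriousness are hard to reconstruct after the fact.

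The outcome codes have a separate fault. One label covers two different things while its definition covers only one of them, and an event that is simply still present at the visit has nowhere to go.

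Assessing side effects is a secondary objective (section 2.2). The risks named in section 6.1 include palpitations, insomnia, gastrointestinal discomfort and anxiety. Such symptoms can occur together and can last beyond a monthly visit, so concurrent and ongoing events are foreseeable in this trial. What is at stake is the completeness and consistency of the safety listing.

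**Working it through.** No arithmetic beyond counting applies. The check sets the planned listing against the form, and then the outcome codes against their definitions.

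**Listing items (section 4.8) against the form (Annexure 1C)**

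| Item promised | Dedicated field on the form |
|---|---|
| Actual term | None; free-text summary only |
| Preferred term | None; normally assigned by later coding, but that needs a recorded actual term |
| Start date | None |
| End date | None |
| ICH E2A category / seriousness | None |
| Relationship | Yes |
| Outcome | Yes, but with the faults below |

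Counting ICH category and seriousness as one item, 2 of 7 items have a dedicated field. Counting them separately, it is 2 of 8. If the preferred term is set aside because it is derived later, four items that must be captured at the visit have no field: actual term, start date, end date and seriousness.

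The degree item does not stand in for seriousness. Section 7.1 defines mild, moderate and severe by tolerability and interference with activity. Severe, for example, is "Any symptom which causes a volunteer's inability to perform usual activity". That is intensity.

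The four numbered items run 1 to 4 without a gap, so the sequence gives no sign of a missing field. The block holds one degree, one relation and one outcome, and the protocol does not say what to do when a participant reports two events of different intensity or relatedness.

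**Outcome codes against definitions (section 7.2)**

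1. *A life-threatening event that the participant survives.* It matches the label "Fatal/Life threatening" but fails the definition, "the subject died as a result of the event". If it has resolved, the definitions send it to one of the recovered codes. The label sends it elsewhere. Section 7.4 treats fatal and life-threatening as alternatives for expedited reporting, so the protocol itself regards them as different.
2. *An event known to be ongoing.* It is not recovered, with or without sequelae. It is not fatal. It is not unknown, because the participant is in follow-up and the status is known. None of the 4 codes applies.

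**The case against.** The best defence is that the protocol does not confine safety data to the tick boxes. The free-text summary can hold a term and dates. Section 7.4 says that all adverse events are collected on the source document. The preferred term needs no box on the form. All of this stands. A reader might infer that the form makes the listing impossible, and the documents do not support that. They support only that these items have no dedicated field and that nothing requires or structures their entry.

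A reader might also infer that deaths could not be told from survived life-threatening events. The definition in section 7.2 bars a survivor from the fatal code, and expedited reports would identify such cases when the reaction is serious and unexpected. The defect is a label at odds with its definition, and the harm is inconsistent coding.

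A third tempting inference is that serious-event reporting or code-breaking would fail. These follow the GCP definition of a serious event and the judgement of medically qualified investigators (sections 7.2 and 7.3). They do not depend on a box on this form.

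Nor can it be said that a second event at a visit is lost. No text forbids a second sheet, and the layout of the annexure is not a safe basis for inferring a limit. The only adverse-event summary figure promised in section 4.8, the percentage of participants with adverse events, comes directly from the yes/no item. No event rates or durations are promised.

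The objection does not reach three things: the absent fields, the contradiction between label and definition, and the missing code for ongoing events.

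**Conclusion.** The point holds in a limited form. Four items that section 4.8 undertakes to list have no dedicated field and depend on unstructured notes. No provision is stated for coding more than one event at a visit. One of the four outcome codes contradicts its own definition, and an event known to be ongoing fits none of them.

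This is a data-capture fault in safety reporting. It should be corrected, but it does not affect randomisation, sample size, power or the primary analysis, and it leaves the route for reporting serious events intact. The conclusion assumes that Annexure 1C is the form to be used and that no separate adverse-event form exists; the protocol's list of annexures names none. If the source documents have their own structured adverse-event log, the first part shrinks to a mismatch between forms. The outcome-code faults would remain, because section 7.2 itself contains them.

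**What to change.** In Annexure 1C, add labelled fields for the verbatim term, start date, end date or ongoing, and seriousness (yes/no, with the criterion met). State that the block is completed once per event. A one-row-per-event table is a convenient layout, but labelled fields on a repeatable sheet would serve equally well.

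In section 7.2 and Annexure 1C, rename the combined outcome code as fatal, keeping the existing death-only definition. Record life-threatening as one of the seriousness criteria. Add an outcome code for not recovered / ongoing.

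The cost is a revision of one annexure and a few lines in section 7.2, plus a minute or two more per reported event. No analysis, sample size or reporting timeline changes. The revision is best made before enrolment, since onset dates and seriousness are hard to recover later.
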